#### 5.5 PHARMACOKINETIC

The PK population will consist of all subjects who receive at least 1 dose of study drug and have sufficient, valid PK samples to estimate key parameters for at least 1 of the days of sampling. PK summaries will be based on the PK population.

#### 5.6 PHARMACODYNAMIC

The PD population will consist of all subjects who receive at least 1 dose of study drug and have sufficient, valid PD samples to estimate key parameters for at least 1 of the days of sampling. PD summaries will be based on the PD population.

## **6 CONSIDERATIONS FOR DATA ANALYSIS**

#### 6.1 PROGRAMMING ENVIRONMENT

All analyses will be conducted using SAS® version 9.2 or higher.

### 6.2 STRATA AND COVARIATES

No covariates will be accounted for in Part 1. In Part 2, analyses will be conducted separately by RAS mutation status (positive or negative).

#### 6.3 SUBGROUPS

There are no planned subgroup analyses.

#### 6.4 MULTIPLE COMPARISONS AND MULTIPLICITY

There are no planned adjustments for multiplicity.

### 6.5 SIGNIFICANCE LEVEL

Unless otherwise noted, all statistical analyses will be conducted with a significance level ( $\alpha$ ) of 0.05 and utilize two-sided testing.

### 6.6 STATISTICAL NOTATION AND METHODOLOGY

Unless stated otherwise, the term "descriptive statistics" refers to the number of subjects (n), mean, median, standard deviation (STD), minimum (min), and maximum (max) for continuous data and frequencies and percentages for categorical data. Min and max values will be rounded to the precision of the original value, means and medians will be rounded to 1 decimal place greater than the precision of the original value, and STDs will be rounded to 2 decimal places greater than the precision of the original value. Percentages will be rounded to the nearest whole number (zeroes are not displayed) with values of "< 1%" and "> 99%" shown as necessary for values falling near the boundaries. P-values will be presented with 3 decimal places and values less than 0.001 will be presented as < 0.001.

Unless otherwise noted, all data collected during the study will be included in data listings and will be sorted by study part (Part 1 or Part 2), subject number, and then by date/time for each subject number. For Part 2, subjects will additionally be sorted by RAS mutation status.

7 DATA HANDLING METHODS

### 7.1 VISIT WINDOWS

All study data will be presented at the nominal visit obtained from the eCRFs, if available. Study day is defined as (date of visit – date of treatment initiation + 1). That is, study day 1 indicates the date of treatment initiation. In the case of early termination visit, the date of the visit will be used to calculate the nominal visit for the analysis.

If there are two or more assessments within a nominal visit, then the assessment that is closest to the scheduled time point/target day will be used in the analysis. If there is more than one closest value, then the evaluation occurring after the target day and prior to the date of last dose will be used in the analysis.

All values will be included in the data listings.

Study visit periods will be windowed as applicable according to the following:

Visit	Nominal Study Day	Study Day Window
Screening		-28 to -1
Baseline	1	N/A
(pre-dose and post-single dose)		(Other visits are scheduled based on this visit)
Cycle 1		
Day 8	8	7 to 9
Day 15	15	14 to 16
Cycle 2		
Day 1	22	21 to 23
Day 8	29	28 to 30
Day 15	36	35 to 37
Cycles 3-X		
Day 1	21*X + 1	-1 to +1

Values will be presented for all scheduled study visits according to the nominal visit obtained from the CRF. If an unscheduled visit falls in a visit window with an existing nominal visit assessment, the nominal assessment will be used for summary presentation. If no nominal visit assessment exists for a visit window with unscheduled visit(s), then the latest unscheduled visit

within the visit window will be used. If multiple nominal assessments are collected within the

same visit, the latest value and corresponding date will be used for summary presentation.

All values will be included in the data listings.

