## 6.5 SAFETY ASSESSMENTS

Safety evaluations will be conducted at baseline, on Days 1, 8, 15, 22, 29, 36, 43, and, in patients who continue treatment, every 3 weeks or if clinically indicated thereafter. These evaluations will include a targeted physical examination, electrocardiography in subjects where clinically indicated and clinical laboratory studies. An ophthalmologic assessment will be conducted at baseline, at the end of study and at other visits by an ophthalmologist if clinically indicated.

The following clinical laboratory tests will be performed:

- **Hematology** (blood sample: EDTA) hemoglobin, hematocrit, white blood cells (WBC) count with differential, red blood cells (RBC) count, and platelet count.
- **Blood Chemistry** (blood sample: serum) albumin, alkaline phosphatase (ALP), total bilirubin, calcium, chloride, creatinine, glucose, inorganic phosphorus, potassium, total protein, alanine aminotransferase (ALT), aspartate aminotransferase (AST), sodium, blood urea nitrogen (BUN) uric acid, cholesterol and triglycerides (at screening and first day of Cycle 1).
- If the total bilirubin concentration is increased above 1.5 times the upper normal limit, total bilirubin should be differentiated into the direct and indirect reacting bilirubin.
- Urinalysis specific gravity, pH; semi-quantitative "dipstick" evaluation of glucose, protein, bilirubin, ketones, leukocytes, and blood and a microscopic examination including RBC, WBC and casts will be performed if the dipstick is abnormal.

Blood chemistry will be analyzed at each trial center by a certified laboratory and a report of the laboratory values will be sent to the trial center. The investigator or designee will review the laboratory report within 24 hours (except during clinic holidays, when review will be performed within 72 hours) after receipt of the results and assess the clinical significance of all abnormal values. Results must be reviewed prior to dosing and appropriate action taken for any clinically significant abnormal values. Values will be documented on the laboratory report until stabilized, or the laboratory value returns to a clinically acceptable range (regardless of relationship to study medication) or baseline. Any laboratory value that remains abnormal at the end-of-study (EOS) and that is considered clinically significant will be followed according to

accepted medical standards for up to 30 days or until resolution of the abnormality or return to baseline.

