## 7.2 DISCONTINUATION OF INDIVIDUAL PATIENTS

Patients are to be withdrawn from the study for any of the following reasons:

- Withdrawal of informed consent
- Disease progression (at the discretion of the PI)
- Unacceptable toxicity
- Changes in the patient's condition which render the patient unacceptable for further treatment in the judgment of the PI
- At least 3 interruptions of BVD-523 intake of > 7 days each, or 8 consecutive days
- Patient becomes pregnant (withdrawal is required)
- Patient is lost to follow-up

Patients will also to be withdrawn at any time if the Investigator concludes that it would be in the patient's best interest for any reason. Protocol violations do not lead to patient withdrawal unless they constitute a significant risk to the patient's safety.

Patients can voluntarily withdraw from the trial for any reason at any time. They are to be considered withdrawn if they state an intention to withdraw, fail to return for visits, became lost to follow up for any reason, or if any of the following occurs:

- Discovery of patient ineligibility
- Significant errors in treatment compliance of at least three interruptions of 7 days each, any treatment interruption of ≥8 consecutive days, or incomplete dosing for greater than 7 days
- Missed / unscheduled / off-schedule / incomplete / incorrect assessments that result in patients being put at risk.

In Part 1 of the study, patients who withdraw at any time due to unrelated AEs preceding the last visit of Cycle 1 (Day 22) will constitute an early discontinuation and must be replaced in order to ensure proper data accrual for dose escalation decisions. A patient who experiences a DLT in Cycle 1 and withdraws before Day 22 either because of the toxicity or otherwise, will nonetheless have that DLT counted in the assessment of potential cohort expansion and/or dose escalation (Table 3.2).

In Part 2 of the study, patients who withdraw at any time preceding the last visit of Cycle 2 (Day 43) will constitute an early discontinuation and will not be replaced and will be evaluated in the Intent to Treat analysis. If patients withdraw due to progressive disease or AEs, replacement of such patients potentially introduces bias into the study. If a patient withdraws for other reasons, replacement of the patient will be decided by the Safety Monitoring Committee.

The investigator must determine the primary reason for a patient's withdrawal from the study and record this information on the eCRF.

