#### 10 SAFETY

Safety analyses will be performed using the Safety Population. Safety will be assessed by examining all adverse events reported during the study including the incidence, and relationship to BVD-523. In addition, safety evaluations will be conducted at Baseline, Days 1, 8, 15, 22, 29, 36, 43, and, in subjects who continue treatment, every 3 weeks or if clinically indicated thereafter. These evaluations will include a targeted ECG where clinically warranted, and clinical laboratory analytes (hematology, chemistry, urinalysis and pregnancy test). An ophthalmologic assessment will also be conducted at baseline, at the end of study and at other visits by an ophthalmologist if clinically indicated.

\*Added as a response option in Note to File dated 21JUL2015

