### 10.8 ECOG PERFORMANCE STATUS

The ECOG performance status is a rating scale used to assess how a subject's disease is progressing as well as how the disease affects the daily living abilities of the subject. The score values are 0-5, where 0 indicates "fully active, able to carry on all pre-disease performance without restriction" and 5 indicates the subject has died. It will be assessed at Screening, Baseline, Study Days 8, 15, 22, 29, 36, 43, and in subjects who continue treatment, every 3 weeks or if clinically indicated thereafter.

The frequencies and percentages of subjects' ECOG performance status will be provided by study visit and dose level treatment group for each study part. A listing of ECOG performance status will also be provided.

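### SAP 7.1 dates Day 1 of Cycles 3-X at 21*X + 1, one cycle late if X is the cycle number, so early-termination visits can be mislabelled in by-visit summaries

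*SAP*

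**What the plan says.** SAP section 7.1 counts study days from treatment initiation as Day 1. Its window table puts Day 1 of Cycle 2 at study day 22 (window 21 to 23). It then gives one row for Day 1 of Cycles 3-X, with nominal day `21*X + 1` and window -1 to +1. X is not defined.

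Three rules decide when the table is used:

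- Data are shown under the eCRF nominal visit where there is one.
- For early termination the date decides: "In the case of early termination visit, the date of the visit will be used to calculate the nominal visit for the analysis".
- An unscheduled result gives way to an existing nominal assessment in its window. Otherwise the unscheduled result is used: "If no nominal visit assessment exists for a visit window with unscheduled visit(s), then the latest unscheduled visit".

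The schedule in SAP Table 3.1 (and protocol Table 6.3) has a Cycle 3-X column with the visit on the first day of each 21-day cycle, starting at Day 43 ± 1.

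For several assessments within one visit, section 7.1 gives two instructions. One is "then the assessment that is closest to the scheduled time point/target day will be used in the analysis", with a tie-break: "the evaluation occurring after the target day and prior to the date of last dose will be used in the analysis". A later sentence says that the latest value is to be used.

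**The concern.** The formula does not return the day on which the SAP itself schedules the visit. A programmer who takes X as the cycle number would build windows one full cycle late from Cycle 3 on.

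This matters where a visit is placed by its date. Protocol section 5.2.6 asks for a treatment discontinuation visit for all patients, so date-based placement is likely to be common rather than exceptional. That visit includes laboratory tests, vital signs, physical examination and ECOG status, which SAP sections 10.4, 10.5, 10.7 and 10.8 summarise by visit or time point. A value taken at discontinuation could appear in the wrong cycle's row, or replace the value that belongs there.

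**Working it through.** **Inputs.** Cycle length is 21 days and cycles are consecutive (SAP 3.1). Study day 1 is Cycle 1 Day 1 (SAP 7.1). Cycle 2 Day 1 is Day 22 (SAP 7.1). The first Cycle 3-X visit is at Day 43 ± 1 (SAP Table 3.1).

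**Step 1: the calendar rule.** With 21-day cycles, Day 1 of cycle c is `21*(c-1) + 1`. For c = 1, 2, 3 this gives 1, 22 and 43, which reproduces the Day 22 in the window table and the Day 43 in the schedule.

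**Step 2: the SAP formula, with X as the cycle number.**

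| Cycle | SAP 7.1, `21*X + 1` | Calendar, `21*(X-1) + 1` | Difference |
|---|---|---|---|
| 3 | 64 | 43 | 21 |
| 4 | 85 | 64 | 21 |
| 5 | 106 | 85 | 21 |
| 6 | 127 | 106 | 21 |

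**Step 3: other references to Day 43.** The schedule column is the explicit evidence. The remaining passages agree with it but do not name Cycle 3. SAP section 10 says "safety evaluations will be conducted at Baseline, Days 1, 8, 15, 22, 29, 36, 43", SAP section 10.8 says "It will be assessed at Screening, Baseline, Study Days 8, 15, 22, 29, 36, 43" and protocol section 6.5 says "Safety evaluations will be conducted at baseline, on Days 1, 8, 15, 22, 29, 36, 43"; each continues at three-week intervals. Protocol section 7.2 refers to "patients who withdraw at any time preceding the last visit of Cycle 2 (Day 43"), that is, the visit that closes Cycle 2. The schedule runs Cycle 2 from Day 22 to Day 42, so Day 43 opens Cycle 3, just as Day 22 both closes Cycle 1 and opens Cycle 2.

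**Step 4: labels by date.** Take the 12 days that are truly Day 1 ± 1 of Cycles 3 to 6 and apply the table as written.

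| Study days | True visit | Label as written |
|---|---|---|
| 42-44 | Cycle 3 Day 1 | none |
| 63-65 | Cycle 4 Day 1 | Cycle 3 Day 1 |
| 84-86 | Cycle 5 Day 1 | Cycle 4 Day 1 |
| 105-107 | Cycle 6 Day 1 | Cycle 5 Day 1 |

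None of the 12 is labelled correctly: 9 carry the previous cycle's label and 3 match no window. These are counts of days, not of expected results.

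**Step 5: one patient.** Suppose a scheduled visit on Day 43 (eCRF label Cycle 3 Day 1) and an early-termination visit on Day 64. The Day 64 visit is also assigned to Cycle 3 Day 1. The table's target is Day 64, so the distances are |64 - 64| = 0 and |43 - 64| = 21. The closest-day rule picks Day 64, and so does the latest-value rule. The real Cycle 3 value can drop out of the summary.

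**Step 6: the duplicate rules, separately from the formula.** For Cycle 2 Day 1 (target Day 22), take values on Days 22 and 23. The closest-day rule picks Day 22 and the latest-value rule picks Day 23. Now take two values on Day 22. They are equally close and neither is after the target day, so the tie-break selects neither. Two values on Day 23 both pass or both fail it. Only the latest-value sentence can settle such same-day repeats.

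**The case against.** **X may mean completed cycles.** In that case X = 2 gives 21 × 2 + 1 = 43 and the formula is right. The schedule also uses X loosely, as an open end for both cycle and visit numbers. This stands to the extent that the authors may have intended the correct days. But nothing defines X that way, and the row label uses it as a cycle number. On either reading the row needs a definition.

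**The reach is narrow.** This stands. Scheduled visits keep their eCRF label. A reader might infer that every unscheduled result near Day 1 of Cycle 4 or later is summarised under the previous cycle. The documents do not support that: where the patient has a nominal assessment for the window, that assessment is used and the unscheduled result is not summarised. The wrong label needs the nominal assessment to be missing.

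**The window entry is clear enough.** On a row with a variable day, -1 to +1 can only sensibly mean an offset from the nominal day. That is fair; rewriting it is for clarity, not correction.

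**Little depends on it.** No formal efficacy analysis is planned and all values are listed. This stands, and it sets the severity.

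**Conclusion.** The point holds as a minor error. With X as the cycle number, the row is 21 days late at every cycle from 3 on and contradicts the SAP's own schedule. It acts mainly through early-termination visits, assuming that these are the discontinuation visits of protocol section 5.2.6. It acts on unscheduled results only where no nominal assessment exists for the window they fall in. How many results would be affected cannot be worked out from the documents.

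Two stronger inferences should be resisted:

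- **That DLT, MTD or response findings are at risk.** Their definitions do not use this table, and the listings show every value.
- **That the formula explains why so many dates fall outside every window.** Of Days 2-126 (125 days), the windows as written cover 15 days up to Day 37, 9 for Cycles 3-5, and Day 126, so 125 - 25 = 100 are uncovered. With the formula corrected they cover 15, then 12 for Cycles 3-6, and Day 126, so 125 - 28 = 97 are uncovered. The formula accounts for 3 days. The rest follows from windows of ± 1 day, and how out-of-window dates are handled is mostly a matter of missing detail.

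The conflict between the two duplicate rules is real but independent of the formula.

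**What to change.** In the SAP 7.1 window table, change the Cycles 3-X row to `21*(X-1) + 1`, define X as the cycle number, and give the window as nominal day ± 1. This yields Day 43 (42-44), Day 64 (63-65), Day 85 (84-86) and so on.

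Separately, replace the two duplicate rules with one ordered rule. For example, take the value closest to the target day first, then the latest value for any remaining tie, including repeats on the same day. The latest-value sentence should not simply be deleted, because the existing tie-break leaves same-day repeats unresolved.

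The cost is one table row, a sentence or two, and a small programming change. No data collection changes.

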## 5.2.6 Treatment Discontinuation Visit

At the time of study drug discontinuation, the Treatment Discontinuation Visit should be completed for all patients as soon as possible after the last dose of study drug, and every effort should be made to perform the procedures required.

Patients will return to the clinic or will be contacted for a safety follow-up assessment 30 days  $\pm$  3 days after the last dose of study drug was taken; or earlier if subsequent therapy for AML or MDS is initiated prior to 30 days  $\pm$  3 days. Only information about AEs and SAEs will be collected at this visit.

The following procedures will be performed at Treatment Discontinuation Visit:

- Review medical history
- Record medications including start/stop dates, indication, dose and frequency.
- Perform and record physical examination.
- Assess and performance status (ECOG).
- Record vital signs. Measure body temperature, systolic / diastolic BP and pulse rate.
- Perform and record ophthalmology examination.
- Perform urine pregnancy test for female patients who are not postmenopausal or surgically sterile. If urine test is positive, collect blood for a serum pregnancy test.
- Assess and record disease status.
- Bone marrow aspirate and/or biopsy. Peripheral, Geimsa and Iron stained slides will be collected with each bone marrow aspirate or biopsy. Collection not needed if termination is due to progression.
- Bone marrow cytogenetics in accordance with local pathology requirements. (Cytogenetics would preferably include at least 20 clones). Collection not needed if termination is due to progression. Collect blood samples for blood chemistries, hematology and creatinine clearance.

- Collect urine samples for urinalysis.
- Assess and record AEs.
- Obtain all unused study drug from patient.
- Assess study drug compliance by reviewing pill count.

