#### Table footnotes:

- a Full medical history at screening, review/update of history only at subsequent visits.
- b Ophthalmological examinations will be performed by an ophthalmologist at screening, at study termination and if clinically indicated.
- c ONLY if the screening serum pregnancy test was performed more than 1 day previously.
- d After screening and baseline, urine pregnancy test which if positive, confirm with serum test.
- Study drug to be taken twice daily, first dose in clinic on days when PK sampling occurs i.e., Cycle 1 on Visit 2 (Day 1) and Visit 5 (Day 22), remaining doses on all other days to be self-administered by patient.
- f PK blood samples will be collected prior to first morning dose and at 0.5 hours, 1 hour, 2 hours, 4 hours, 6 hours, 8 hours and 12 ±2 hours post-dose. Pharmacodynamic and peripheral blood mononuclear cells (PBMC) blood samples will be collected prior to first morning dose and at 4 hours post-dose.
- Pharmacodynamic, PK and PBMC blood samples are required at baseline where feasible. Additional biomarkers and DNA sequence analysis may be identified and measured as appropriate by collection of whole blood prior to dosing initiation and after drug levels have reached steady-state. Steady state refers to patients who have received at least 5 days, or 10 consecutive doses, of investigational product. If patients are not at steady state, these assessments will be rescheduled and completed at the next visit in which steady state is achieved. Leukemic cell genotyping by DNA analysis may be performed to identify somatic alterations, relying on either available stored samples or freshly collected samples.
- h Bone marrow aspirate and/or biopsy. Peripheral, Geimsa and Iron stained slides to be provided with each bone marrow aspirate or biopsy. Bone marrow aspirate and/or biopsy slides will not be shipped to a third party. As such, the site may utilize BM aspirates performed in clinical practice as SOC, as long as they are collected within the screening window (-28 days). Bone marrow cytogenetics (cytogenetics should include at least 20 clones). Bone marrow aspirates may be used to evaluate biomarkers of drug response.
- i Chemistry (to include calcium and inorganic phosphorus), hematology and urinalysis. After Cycle 2, clinical chemistry (to include calcium and inorganic phosphorus), hematology and urinalysis may be performed once per cycle or more frequently at the investigator's discretion.

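### SAP 7.1 assigns early-termination visits by date to three-day windows that leave most days uncovered, so discontinuation values may have no analysis visit or an arbitrary one

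*SAP*

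**What the plan says.** SAP 7.1 opens with a general rule: "All study data will be presented at the nominal visit obtained from the eCRFs, if available". It then sets early-termination visits apart: "In the case of early termination visit, the date of the visit will be used to calculate the nominal visit for the analysis".

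The window table in the same section gives Days 7-9, 14-16, 21-23, 28-30 and 35-37 for Cycles 1 and 2, then one day either side of the first day of each later cycle. It has no row for a final or early-discontinuation visit. The section does not say what happens to a date that lies in no window.

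Three further rules in SAP 7.1 bear on a visit that does land in a window:

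- Where two or more assessments share a nominal visit, "the assessment that is closest to the scheduled time point/target day will be used in the analysis".
- At the end of the section, where several nominal assessments belong to one visit, "the latest value and corresponding date will be used for summary presentation".
- For unscheduled visits, "If an unscheduled visit falls in a visit window with an existing nominal visit assessment, the nominal assessment will be used for summary presentation".

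Elsewhere the plan treats the final visit as a time point of its own. SAP Table 3.1 gives Final Study Visit/Early Discontinuation its own column, and SAP 10.9 names the Final Study Visit for marrow collection. Protocol 5.2.6 says that the discontinuation visit "should be completed for all patients as soon as possible after the last dose of study drug". On eye exams, footnote b of SAP Table 3.1 reads: "Ophthalmological examinations will be performed by an ophthalmologist at screening, at study termination and if clinically indicated".

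**The concern.** The date of a discontinuation visit is set by when the patient stops, not by the cycle grid. A rule that discards its label and looks up its date in narrow, separated windows will often find nothing. When it does find a window, the result is shown as an ordinary on-treatment visit and has to compete with the scheduled assessment there.

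The tables exposed are those built by visit or time point: laboratory values and changes from baseline (SAP 10.4), vital signs and weight (10.5), physical examination (10.7) and ECOG (10.8). The SAP describes no last-value or worst-post-baseline summary that would clearly recover the results, and it states no time point for the laboratory shift tables. Patients leave for reasons that include progression, unacceptable toxicity and a change in condition (Protocol 7.2), so values taken at that moment are informative.

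Ophthalmology deserves separate mention. Protocol 1.5.1 names ocular toxicity as a potential class risk, and the termination exam is the only one scheduled after baseline. If Table 14.3.5.4 is laid out by visit, the SAP 7.1 rule either gives that exam no visit or attaches it to a visit at which no eye exam is scheduled.

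**Working it through.** The documents give no figure for window coverage, so there is none to reproduce. The check is a direct count.

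**Inputs**
- Windows for Cycles 1 and 2, from SAP 7.1: Days 7-9, 14-16, 21-23, 28-30, 35-37.
- Cycle 3 Day 1: Day 43 ± 1 in SAP Table 3.1. The SAP 7.1 formula 21*X + 1 gives 21 × 3 + 1 = Day 64 if X is the cycle number. Both readings are counted.
- Discontinuation can fall on any day from Day 2.

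**Days 2-42, Cycle 3 Day 1 = Day 43**
- Covered: 5 windows × 3 days = 15, plus Day 42 (the first day of the 42-44 window) = 16 of 41.
- Uncovered: 41 − 16 = 25; 25/41 = 61%.
- Cross-check by gaps: Days 2-6 (5 days), then 10-13, 17-20, 24-27, 31-34 and 38-41 (4 days each): 5 + 5 × 4 = 25.

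**From Cycle 3 on**
- Each 21-day cycle has one 3-day window. Uncovered: 21 − 3 = 18; 18/21 = 86%.

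**Other horizons and the literal formula**

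| Days | Covered, Cycle 3 = Day 43 | Uncovered | Covered, Cycle 3 = Day 64 | Uncovered |
|---|---|---|---|---|
| 2-42 | 16 of 41 | 61% | 15 of 41 | 63% |
| 2-84 | 22 of 83 | 73% | 19 of 83 | 77% |
| 2-126 | 28 of 125 | 78% | 25 of 125 | 80% |

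On the literal reading, Days 38-62 (25 consecutive days) have no window at all. Most days are uncovered on either reading.

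**From days to patients**

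The documents do not say how stopping dates are distributed. Suppose a fraction c of patients have their discontinuation visit inside a scheduled window because the decision is taken there, and the rest stop on days unrelated to the grid. The share with no window is then (1 − c) × (uncovered share of days).

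| c (assumed) | Stopping in Days 2-42 | Stopping from Cycle 3 |
|---|---|---|
| 0 | 61% | 86% |
| 0.5 | 0.5 × 25/41 = 30% | 0.5 × 18/21 = 43% |
| 1 | 0% | 0% |

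**Inside a window**

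Take Visit 5 on Day 22 and a discontinuation visit on Day 23, with target Day 22. The distances are 0 and 1, so the closest-to-target rule keeps Day 22 and drops the discontinuation value from the table. The latest-value rule keeps Day 23 and drops the scheduled value. When distances tie, SAP 7.1 prefers an assessment made after the target day but before the last dose. A discontinuation visit normally follows the last dose and would normally fail that test. The choice between scheduled and discontinuation value is therefore not settled in advance, and either way one of two differently timed measurements is lost from the table.

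**The case against.** A reader might infer that the SAP drops discontinuation values from the summaries altogether, and that the safety profile will therefore look better than it is. The text does not go that far, and several points against it stand.

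- SAP 7.1 nowhere says that an out-of-window value is excluded. Its wording presupposes that a nominal visit can be calculated, and assignment to the nearest visit would be compatible with it. The eCRF-label default and the Final Study Visit in SAP 10.9 also leave room for a separate label. But the early-termination sentence would have no function if the eCRF label were meant to stand.
- Some discontinuation dates do fall in a window. Disease status and marrow are assessed at Day 22 and every other cycle thereafter, so decisions to stop may cluster at scheduled visits.
- Table 14.3.5.4 appears only as a title, and the shells are in a separate attachment. The opening of SAP 10 treats end of study as a time point for ophthalmology. It cannot be said that the table loses its post-baseline column.
- The main safety outputs do not use these windows: treatment-emergent events up to 30 days after the last dose, highest severity per patient, serious events, deaths, DLTs and exposure. On listings SAP 7.1 says: "All values will be included in the data listings".
- That the discontinuation visit holds each patient's worst values is plausible but not documented.
- The ±1-day windows match the protocol's visit tolerances. Leaving off-window unscheduled results to the listings is a legitimate choice.

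These points limit the consequence. They do not supply a rule for the dates outside every window, or a reason to relabel a visit that the schedule already names.

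**Conclusion.** The point holds as a defect in the visit-mapping rule. SAP 7.1 replaces a usable label with a date lookup that has no answer for 61% of Days 2-42 and 86% of days from Cycle 3, taking Cycle 3 Day 1 as Day 43. Those are shares of days. They become shares of patients only if stopping dates are unrelated to the visit grid, and are lower if stopping clusters at scheduled visits.

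The consequence is that discontinuation values may be left out of the by-visit laboratory, vital-sign, physical-examination and ECOG summaries, or shown at an arbitrary on-treatment visit. The same may happen to the termination eye exam if Table 14.3.5.4 is by visit. The documents do not establish that these values are lost or that the overall safety picture is distorted. Listings and the adverse-event, DLT and exposure summaries stay intact. The change should still be made, because it is cheap and the affected tables are planned outputs. The problem would remain even if the later-cycle formula and the conflict between the closest and latest rules were corrected.

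**What to change.** Delete the SAP 7.1 sentence that recalculates the nominal visit for early termination. In its place, state that assessments at Final Study Visit/Early Discontinuation form their own analysis visit, as in SAP Table 3.1, and do not compete with scheduled values under the repeat-assessment rules. Show that visit in the by-visit laboratory, vital-sign, physical-examination and ECOG tables, and in the ophthalmology table, whose layout should be stated.

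Every discontinuation visit then has a place, whatever its date. The cost is SAP wording and one extra row or column per table, with no new data or procedures. Contiguous windows, split at midpoints between target days, would also give off-schedule unscheduled results a visit, but they are optional and not needed for this fix.
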